1.1.2 Secondary Objectives

- Determine morbidity of this procedure in this patient population
- Determine the impact of surgery and HIPEC on QOL
- Determine the impact of surgery and HIPEC on hormone excess
- Examine patterns of recurrence (local versus systemic)
- Perform molecular analyses to try to discern if there are intrinsic differences between tumors that recur widely throughout the peritoneal surface and those that metastasize to other organs or are confined to a local recurrence.
- Determine overall survival after optimal debulking and heated intraperitoneal chemotherapy with cisplatin in patients with intraperitoneal spread of adrenocortical cancer.

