1.2 BACKGROUND AND RATIONALE

1.2.1 Adrenocortical Carcinoma

Adrenocortical carcinoma (ACC) is a rare tumor with an incidence of 1.5 to 2 per million people per year¹⁻³. It has a very poor prognosis with an overall 5-year mortality rate of 75 - 90% and an average survival from the time of diagnosis of 14.5 months. Signs and symptoms due to excess hormonal secretion are seen in a large fraction of patients, further contributing to the morbidity associated with this disease.

The treatment of choice for a localized primary or recurrent tumor is surgical resection. Excisable primary tumors represent about 40% of cases at presentation; however, 60 - 80% of these patients eventually die from recurrent extensive metastases⁴. Patients with recurrent or metastatic disease are infrequently curable by surgery alone due to the propensity for intraperitoneal recurrence.

For unresectable metastatic or recurrent disease, mitotane, aminoglutethimide, metapyrone, and ketoconazole are used. Of these, mitotane is the only agent with both anti-tumor and adrenolytic effects. Aminoglutethimide, metapyrone, and ketoconazole are used to treat the symptoms of excess hormone production in patients with functional tumors. Mitotane, the most extensively studied agent, was reported to have response rates of 30-60% in older studies without standardized response criteria or the use of modern imaging technology⁵⁻⁷. Response rates of 20% or less have been noted with more modern imaging technology. These responses persist for an average of 10.5 months with no apparent impact on overall survival.

Most reports of cytotoxic therapy for ACC are anecdotal or include a small number of patients⁸⁻¹³. These studies report low response rates with the majority of responses classified as partial and

of less than one year in duration. Trials using mitotane in combination with various chemotherapeutic agents have had similar results^{12, 13}. The largest randomized trial for metastatic or locally advanced ACC conducted was recently published and showed that a regimen of etoposide, doxorubicin and cisplatin (EDP) combined with mitotane was superior to the combination of streptozocin and mitotane with a median PFS of 5.0 months vs. 2.1 months and response rate of 23.2 and 9.2% respectively¹⁴.

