3.11 TREATMENT ASSESSMENT AND RESPONSE (FOLLOW UP PERIOD)

- Because of the nature of peritoneal imaging and because cytoreductive surgery will likely eliminate all imageable disease, response can only be measured in terms of radiographic disease-free survival. At any time point when there is evidence of progressive disease (imageable tumor nodules or increasing ascites persistent on CT scans as interpreted by the official interpretation of the imaging studies) the patients will be scored as progressive disease. In some cases this may require successive scans, but the time of

recurrence will be retrospectively defined at the point the first scan demonstrated imageable disease.

- Patients will be evaluated 3 months from the operative date (+/- 1 month) intervals for the first year; every four months for (+/- 1 month) the next year and then q 6 months (+/- 1 month) thereafter.
- The following evaluations will be performed at each visit:
 - Imaging studies
 - Physical examination to include ECOG, weight and vital signs
 - Tumor markers as indicated
 - CBC, acute care, mineral and hepatic panel, CRP, Albumin, pre-albumin, ferritin, Hgb A1c if elevated pre-op.
 - Completion of Health related Quality of Life Forms (HRQOL) – at the first follow up visit and then at each evaluation until off study.
- Patients who are unwilling or unable to return for follow up evaluation will be followed every 6 months by phone contact until off study criteria are met. The following information may be obtained:
 - Summary of treatment received since the previous contact
 - Estimation of ECOG status
 - Request for imaging studies, physical exam and laboratory reports to be sent to the PI

Note: if patient is taken off study prior to 1 year following surgery, the HRQOL will be completed at the off study evaluation if possible.

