3.13.2 Off Study Criteria

- Death
- Disease progression requiring systemic therapy
- Start of any therapeutic agent other than mitotane
- Completed study follow-up period
- Participant requests to be withdrawn from the study
- Lost to follow up
- PI decision to close the study

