7 SAFETY REPORTING REQUIREMENTS/DATA AND SAFETY MONITORING PLAN

7.1 DEFINITIONS

7.1.1 Adverse Event

An adverse event is defined as any reaction, side effect, or untoward event that occurs during the course of the clinical trial associated with the use of a drug in humans, whether or not the event is considered related to the treatment or clinically significant. For this study, AEs will include events reported by the patient, as well as clinically significant abnormal findings on physical

examination or laboratory evaluation. A new illness, symptom, sign or clinically significant laboratory abnormality or worsening of a pre-existing condition or abnormality is considered an AE. All AEs must be recorded on the AE case report form unless otherwise noted above in Section 6.3.2.

All AEs, including clinically significant abnormal findings on laboratory evaluations, regardless of severity, will be followed until return to baseline or stabilization of event. Serious adverse events that occur more than 30 days after the last administration of investigational agent/intervention and have an attribution of at least possibly related to the agent/intervention should be recorded and reported as per section 7.2.

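### The off-study rule is not limited to anticancer drugs, so starting a hormone-control drug could end observation before radiographic progression and lengthen apparent PFS

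*Combined protocol and SAP*

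**What the plan says.** Section 3.13.2 lists among its off-study criteria "Start of any therapeutic agent other than mitotane". Progression has its own entry, "Disease progression requiring systemic therapy", so the drug criterion operates without it. The term is not defined, and mitotane is the only exemption.

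Section 1.2.1 says of three other drugs: "Aminoglutethimide, metapyrone, and ketoconazole are used to treat the symptoms of excess hormone production in patients with functional tumors". It describes mitotane as the only drug in that group that acts on the tumor as well as on the adrenal. It also says "Signs and symptoms due to excess hormonal secretion are seen in a large fraction of patients", without giving a number. One secondary objective in section 1.1.2 is "Determine the impact of surgery and HIPEC on hormone excess".

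Under section 3.11, "response can only be measured in terms of radiographic disease-free survival", and recurrence is dated to the first scan that shows disease. Patients who cannot attend "will be followed every 6 months by phone contact until off study criteria are met". Section 9.5 presents surveillance for recurrence as a benefit of remaining on study.

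Section 8 compares median PFS with a historical 5.0 months, targets 10 months, and plans Kaplan-Meier curves with confidence intervals. It does not say how a patient who goes off study without progression is analysed.

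**The concern.** The primary endpoint depends on scans, and the drug criterion can end scanning for a reason other than progression. In a functional tumor, one reason to start a hormone-control drug is that hormone excess has come back. If that sometimes happens before recurrence can be seen on imaging, the patients removed are those closest to an event. Kaplan-Meier assumes that censored patients have the same future risk as those who remain. Here their risk would be higher, and the curve would be too optimistic. The trial has one arm and is judged against a historical figure, so no control group shares the bias.

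The hormone-excess objective is also affected, because hormone measurements after exit would not be collected for these patients.

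**Working it through.** **Step 1: what the criterion covers.** Four places bear on its scope.

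- Section 1.2.1 names three non-mitotane drugs given for hormonal symptoms. Each is a therapeutic agent in the ordinary sense, so starting one meets the criterion as worded.
- Section 4 provides antibiotics and other supportive care after surgery.
- Section 6.2.2 expects as-needed drugs and drugs that treat adverse events. Taken literally, section 3.13.2 would remove patients for these as well.
- Section 2.1.1 also exempts mitotane, but there the exemption is attached to prior chemotherapy, immunotherapy and radiotherapy.

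The literal reading therefore cannot be fully intended, but no passage states a narrower one. Staff who apply the wording differently would censor different patients.

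**Step 2: what happens after exit.** Section 3.11 ends telephone contact when off-study criteria are met. Section 9.5 links surveillance to being on study, and no section provides scans afterwards. The visit schedule itself carries no explicit off-study limit, so the end of scanning is an inference, though a well-supported one. Censoring is likewise the probable handling, not a stated one.

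**Step 3: the plan's own figure.** Inputs from section 8: n = 24, null median 5 months, target 10 months, one-sided alpha 0.10. Under an exponential with median 10 months, S(5) = 0.5^0.5 = 0.7071. The normal approximation to the Brookmeyer-Crowley test of S(5) = 0.5 gives

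power = Φ[(0.7071 − 0.5 − 1.2816 × √(0.25/24)) / √(0.7071 × 0.2929/24)] = Φ[(0.2071 − 0.1308)/0.0929] = 0.794.

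The stated 80% reproduces and is not in dispute.

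**Step 4: illustration of the bias.** Assumptions, none of them in the documents: exponential PFS with true median 5 months, so λ = ln 2/5 = 0.1386. A share f of patients leaves L months before scored progression and is censored then. Those in this share who progress within the first L months are still observed.

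With a = f·e^(−λL):

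- the cumulative hazard that Kaplan-Meier estimates up to L is H = −ln[e^(−λL)(1 + a) − a]/(1 + a);
- after L the apparent hazard is constant at h = λ(1 − f)/(1 − f + a);
- the apparent median is L + (ln 2 − H)/h.

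Example, f = 0.2 and L = 1: a = 0.2 × 0.8706 = 0.1741, H = 0.1404, h = 0.1139, and the median is 1 + (0.6931 − 0.1404)/0.1139 = 5.85 months.

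| Lead L | Share f | Apparent median (months) | Apparent PFS at 5 months | False-positive rate, n = 24 |
|---|---|---|---|---|
| none | 0 | 5.0 | 50% | 0.08 |
| 1 month | 10% | 5.4 | 52.5% | 0.14 |
| 1 month | 20% | 5.9 | 55% | 0.22 |
| 1 month | 30% | 6.5 | 58% | 0.31 |
| 2 months | 10% | 5.2 | 51.5% | 0.12 |
| 2 months | 20% | 5.5 | 53% | 0.17 |
| 2 months | 30% | 5.9 | 55% | 0.21 |

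The last column is from simulation (40,000 trials per row) of a one-sided test of the Kaplan-Meier estimate at 5 months with Greenwood variance, as a stand-in for the planned test. If patients who would progress within the lead time are also removed, at the outset, the rates are higher: about 0.16, 0.24 to 0.26, and 0.36 to 0.39 for shares of 10%, 20% and 30%. The bias is largest when exit comes just before progression.

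**The case against.** The strongest reply is that the criterion was meant for anticancer drugs. The parallel exemption in section 2.1.1 points that way, and sections 4 and 6.2.2 make a rule against every drug unworkable. This stands as evidence of intent. It does not remove the problem, because the operative wording is unrestricted and hormone-control drugs fall in the gap between the two readings.

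The size is also open to objection. The documents give no rate of starting these drugs and no lead time. The large fraction in section 1.2.1 describes the disease in general, not patients after debulking. A patient already taking such a drug does not start it. Markers and imaging are assessed at the same visits, so the unscanned interval may be short. With 24 patients, 10% is two or three people, and a shift of 0.2 to 1.5 months is small beside the planned 5-month difference. All of this stands: the table shows direction and possible size, not an estimate.

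Three stronger readings are tempting, and the documents do not support them.

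- A reader might infer that adverse-event follow-up stops at exit. Section 7.1.1 says that events, "regardless of severity, will be followed until return to baseline or stabilization of event", with no off-study cut-off, and it also covers late serious events that are at least possibly related.
- A reader might infer that the rule strikes out patients with returning hormone excess from that objective. Nothing discards data gathered before exit, and the return itself can be observed on study. Only later hormone data are lost.
- A reader might take it as established that those removed have returning disease. No section says that hormone excess precedes imageable recurrence.

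**Conclusion.** The concern holds as a fault in a stated rule. As worded, section 3.13.2 can end observation when a symptomatic drug is started, and section 8 does not say how such a patient is analysed. Any resulting bias would favour the treatment if hormonal return sometimes comes before a positive scan.

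Under the assumed shares of 10% to 30% and leads of 1 to 2 months, a true median of 5 months appears as about 5.2 to 6.5 months. That alone would not look like the 10-month target, but in the same illustration the false-positive rate rises from about 0.08 to between 0.12 and 0.31. These figures rest on exponential PFS, on censoring at exit, and on rates that the documents do not supply. The change is worth making because it is cheap and the rule touches the primary endpoint.

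**What to change.** - In section 3.13.2, limit the criterion to the start of anticancer therapy other than mitotane, and state that hormone-control and supportive drugs do not end observation. Reconcile the wording with sections 1.2.1, 2.1.1, 4 and 6.2.2. This settles who stays under observation, not what anyone should receive.
- Record the start date of hormone-control drugs. This has to be a stated exception to section 6.2.2, which captures drugs begun after baseline only if they cause an adverse event. The hormone-excess analysis can then take the drugs into account.
- In section 8, add a sensitivity analysis for patients who leave without radiographic progression, for example one that counts the exit as progression, reported beside the main estimate.

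The cost is one line of wording, one data field, a short addition to the analysis text, and a few patients followed longer on the existing visit schedule.

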3.13.3 Off Protocol Therapy and Off Study Procedure

Authorized staff must notify Central Registration Office (CRO) when a subject is taken off protocol therapy and when a subject is taken off-study. A Participant Status Updates Form from the web site (<http://home.ccr.cancer.gov/intra/eligibility/welcome.htm>) main page must be completed and sent via encrypted email to: NCI Central Registration Office [contact].

4 CONCOMITANT MEDICATIONS/MEASURES

During the post-operative period, patients will receive all standard of care supportive measures including possible nasogastric tube drainage and bowel rest for ileus, pulmonary toilet teaching and incentive spirometry to prevent atelectasis, transfusions, and antibiotics as indicated.

5 BIOSPECIMEN COLLECTION

No specimens will be collected for future research purposes on this protocol. Patients who are willing to have specimens collected for future research purposes will be co-enrolled on protocol 13-C-0176.

6 DATA COLLECTION AND EVALUATION

6.1 DATA COLLECTION

The PI will be responsible for overseeing entry of data into an in-house password protected electronic system and ensuring data accuracy, consistency and timeliness. The principal investigator, associate investigators/research nurses and/or a contracted data manager will assist with the data management efforts. All data obtained during the conduct of the protocol will be kept in secure network drives or in approved alternative sites that comply with NIH security standards. Primary and final analyzed data will have identifiers so that research data can be attributed to an individual human subject participant.

End of study procedures: Data will be stored according to HHS, FDA regulations, and NIH Intramural Records Retention Schedule as applicable.

Loss or destruction of data: Should we become aware that a major breach in our plan to protect subject confidentiality and trial data has occurred, the IRB will be notified.

Data will not be distributed outside NIH without IRB notification.

[name] will continue to have access to the data for purposes of data analysis and publication when she is at Eastern Virginia Medical. She will also have access to the data via a secure flash drive. It is also possible that data will be sent to her via encrypted email. [name] involvement in this research is covered under the Federal Wide Assurance of the NIH.

6.2 ROUTINE DATA REPORTING

6.2.1 Laboratory events will be captured as follows

- During hospitalization for surgical resection, only the admission labs, first morning labs drawn after 4am, and labs that support the diagnosis of a reportable event will be uploaded into C3D.
- For laboratory values obtained at sites other than the NIH Clinical Center: only the following values (highest grade per cycle) will be captured in C3D:
 - Hemoglobin, total white blood cell count, absolute neutrophil count, platelet count
 - PTT, PT or INR
 - Creatinine, ALT, AST, Bilirubin (total and direct),
 - Any unexpected laboratory abnormality \geq grade 2 possibly, probably or definitely related to the research

6.2.2 Concomitant Measures and Medications

- Only those medications that the patient is taking at baseline on a routine basis or medications that cause an AE will be captured in C3D. [Thus onetime medications, PRN medications, and medications given to treat adverse events will not be captured in C3D.]
- Vital signs will be captured once at baseline
- Evaluations that are performed for clinical indications only will not be captured (e.g. daily chest x-rays during hospitalization, interim post op visits)

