2 ELIGIBILITY ASSESSMENT AND ENROLLMENT

2.1 ELIGIBILITY CRITERIA

2.1.1 Inclusion Criteria

- Histologically proven ACC with the majority of disease confined to the peritoneal cavity and resectable or amenable to radiofrequency ablation
- Disease evaluable by CT or PET imaging
- All disease should be deemed resectable based on imaging studies e.g.:
 - Hepatic metastases (unilateral or bilateral ≤ 5 lesions, ≤ 15 cm total diameter)
 - **Note:** Hepatic lesions must be amenable to complete resection
 - Primary peritoneal metastases (small disease load $\leq P2$ disease) without massive ascites or intestinal obstruction
 - Lung metastases (≤ 3 unilateral/bilateral, 9 cm total diameter)
 - **Note:** lung lesions must be amenable to complete resection
 - **Note:** Patients with both pulmonary and hepatic metastases will be enrolled at the discretion of the PI
 - **Note:** In situations where resection to Completeness of Cytoreduction Score (CC) 0 or 1 is uncertain, patients may undergo diagnostic laparoscopy prior to enrollment to determine feasibility of resection. (**Appendix D**)
- Greater than or equal to 18 years of age
- Able to understand and sign the Informed Consent Document

- Clinical performance status of ECOG ≤ 2
- Life expectancy of greater than three months
- Patients of both genders must be willing to practice birth control during and for four months after receiving chemotherapy
- Hematology:
 - Absolute neutrophil count greater than 1500/mm³ without the support of Filgrastim.
 - Platelet count greater than 75,000/mm³.
 - Hemoglobin greater than 8.0 g/dl.
- Chemistry:
 - Serum creatinine less than or equal to 1.5 mg/dl unless the measured creatinine clearance is greater than 60 mL/min/1.73 m²
 - serum AST and ALT within 5 times the upper limit of normal and a total serum bilirubin of less than 3 times the upper limit of normal, both of which define the upper limit of grade 2 treatment related toxicities.
 - PT within 2 seconds of the upper limit of normal (INR \leq 1.8)
- Recovered from any toxicity to grade 2 or less from all prior chemotherapy, immunotherapy or radiotherapy and be at least 30 days past the date of their last treatment with the exception of mitotane which may be continued.
- Able to understand their disease and the exploratory nature of combining surgery and HIPEC for this histology.

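### Mitotane can be started or changed after HIPEC without leaving the study, but the database has no routine place to record it, so later hormone-excess values cannot be attributed to surgery and HIPEC from the database alone

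*Combined protocol and SAP*

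**What the plan says.** - **Entry (2.1.1).** Prior anticancer treatment must have ended at least 30 days earlier, "with the exception of mitotane which may be continued".
- **Off-study rules (3.13.2).** One criterion is "Start of any therapeutic agent other than mitotane". A separate one is "Disease progression requiring systemic therapy".
- **Database rule (6.2.2).** "Only those medications that the patient is taking at baseline on a routine basis or medications that cause an AE will be captured in C3D". C3D is the study database.
- **Follow-up (3.11).** Each visit covers imaging, physical examination, tumour markers as indicated, blood tests and quality-of-life forms. Medication is not listed. The only treatment query is "Summary of treatment received since the previous contact". It belongs to the telephone route ("Patients who are unwilling or unable to return for follow up evaluation will be followed every 6 months by phone contact"), and the protocol says only that this information may be obtained.
- **Activity of the drug (1.2.1).** Among the agents listed for unresectable or recurrent disease, "mitotane is the only agent with both anti-tumor and adrenolytic effects".
- **Objective affected (1.1.2).** "Determine the impact of surgery and HIPEC on hormone excess".
- **Analysis (2.4 and 8).** Stratification is by peritoneal recurrence only versus visceral metastatic disease. Section 8 describes a single-arm comparison with a 5.0-month median PFS on EDP plus mitotane. Neither section has a rule for mitotane exposure.

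**The concern.** The protocol permits an active drug to begin during follow-up, and its stated capture rule leaves that drug out of the database. Mitotane lowers hormone production directly, so a patient whose cortisol falls some months after surgery may owe the fall to the operation, to the drug, or to both. With no control arm, exposure data are the only means of telling these apart. The hormone objective has no historical benchmark either, so nothing offsets the problem. For PFS the same gap means the final report could not say from the database how many patients received further anti-tumour treatment before progression.

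**Working it through.** **1. Can a post-operative mitotane start or change reach the database?** Taking each route in turn:

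| Route | Does it capture the start or change? |
|---|---|
| Routine baseline medication (6.2.2) | Use at baseline, yes. A later start, no. No rule asks for later dose changes or a stop date. |
| Medication that causes an AE (6.2.2) | Only if such an AE is captured. Section 6.3.2 keeps grade 1 and 2 events after discharge out of C3D. More than 30 days after treatment it admits only events that are serious, unexpected and related to treatment. |
| Clinic visit (3.11) | No medication item. |
| Telephone contact (3.11) | Optional, and only for patients who do not return. |
| Off-study form (3.13.2) | Starting mitotane is exempt. Progression requiring systemic therapy does end participation, so the gap chiefly concerns mitotane before progression, which is the period PFS measures. |

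No route captures it routinely.

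**2. Which hormone values are exposed?** Markers are taken, as indicated, within 2 weeks before treatment (2.2.3), on the day of discharge as a new baseline (3.7.1), on recovery after a first visit at about 4 to 8 weeks (3.10), and at each follow-up visit (3.11). With a stay of about 7 to 14 days (3.9), the change from pre-operative to discharge leaves little time for a new drug to act. The recovery value is less protected and the later values are open.

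**3. The plan's own PFS figure.** Inputs from section 8: n = 24, medians 5 and 10 months, one-sided alpha 0.10, stated power 80%. Treat the Brookmeyer-Crowley method as a test of S(5 months) = 0.50, with exponential PFS and no censoring before 5 months.

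- S(5) under the alternative = 0.5^(5/10) = 0.7071.
- Power = Φ[(0.7071 − 0.50 − 1.2816 × √(0.25/24)) / √(0.7071 × 0.2929/24)] = Φ[(0.2071 − 0.1308)/0.0929] = 79.4%.

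The stated 80% reproduces.

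**4. Direction of a PFS bias.** Uptake and hazard ratio are assumptions here; the documents give neither. Suppose half the patients start mitotane at surgery, with hazard ratio h, and apply the same test. P(success) = Φ[(S − 0.50 − 0.1308)/√(S(1 − S)/24)].

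- *Case A: true median 5 months without mitotane.* S(5) = 0.5 × 0.5 + 0.5 × 0.5^h. For h = 0.80, S = 0.537 and P = 18%. For h = 0.67, S = 0.564 and P = 26%.
- *Case B: true median 5 months with mitotane, as in the benchmark regimen.* Patients without it then have median 5h (4.0 or 3.35 months), and S(5) = 0.5 × 0.5 + 0.5 × 0.5^(1/h). For h = 0.80, S = 0.460 and P = 5%. For h = 0.67, S = 0.428 and P = 2%.

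The nominal rate is 10%. The same drug effect moves it up or down according to what the 5.0-month figure is taken to represent. These figures show only that the sign is undetermined; they do not estimate the bias.

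**The case against.** Section 6.2.2 restricts what enters C3D, not what is kept in source documents. For 24 evaluable patients, chart review might recover one drug's dates. A reader might infer that exposure will be unknowable, and the documents do not support that. What stands is that recovery is not assured: section 3.10 lets post-discharge blood counts be done through the referring physician, and section 3.11 allows follow-up by telephone.

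The protocol does not plan or predict new mitotane starts. It only exempts them from an off-study rule, and patients already on mitotane appear at baseline. Staff must also ask about new therapy in order to apply that rule. All this is fair and limits the likely extent, but the exemption is explicit and none of it creates a data field.

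A reader might also infer that PFS will look falsely long. The benchmark came from a mitotane-containing regimen, so exposure here is not a one-sided advantage, and Case B above shows the reverse effect. That argument does not reach the hormone objective.

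Nor can a share of the hormone data be declared confounded. The documents give no uptake figure, only patients with hormone excess inform that objective, and markers are drawn as indicated. The response rate of 20% or less in section 1.2.1 concerns unresectable metastatic or recurrent disease and measures neither hormone change nor PFS after resection.

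**Conclusion.** The point holds as a gap in data capture with a specific consequence. Under the stated rules, a mitotane start or dose change after HIPEC is not routinely in the study database. Hormone values after the early post-operative measurements therefore cannot be attributed to surgery and HIPEC from that database alone. The pre-operative and discharge values are less affected.

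For PFS, the gap leaves the result harder to interpret, with no determinable direction. The size of either effect cannot be estimated from the documents. The conclusion rests on reading 6.2.2 literally and on the protocol's own description of mitotane as adrenolytic. It does not assume that many patients will start the drug. This is a minor, inexpensive improvement and does not threaten the primary test.

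**What to change.** - **Capture.** Amend section 6.2.2 to record start, stop and dose-change dates at baseline and at each follow-up contact, for mitotane and for any hormone-lowering drug taken at baseline.
- **Hormone excess.** Report the change from the pre-operative value at discharge and at the first recovery visit. Report later values descriptively in two ways: overall, and using only measurements taken before any such drug was started or increased. Say plainly that the second set selects on a post-treatment decision, which hormone levels may themselves have prompted.
- **PFS.** State beside the PFS result how many patients started mitotane before progression. If PFS is described by exposure, use a landmark or time-dependent description labelled exploratory. A simple table by ever-use would carry immortal-time bias, because a patient must stay progression-free long enough to start the drug.

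The cost is a few added form fields and a small descriptive table. The sample size and primary test do not change, and no change to who may receive mitotane is implied.
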